1 INTRODUCTION

Contact lens (CL) discomfort affects up to 50% of contact lens wearers.¹ Patients with signs and symptoms of dry eye disease (DED) have significantly increased odds of dropping out of CL wear.¹ It is likely that symptomatic CL wearers also have DED, either due to evaporative causes, aqueous deficiency or, most often, a combination of both.

To date, there are no CL studies characterizing dry eye in CL wearers using the TFOS DEWS II guidelines.²

2 OBJECTIVES

The objectives of the study are:

- To examine and classify DED subtypes in a group of symptomatic CL wearers who are already wearers of daily disposable (DD) CLs (excluding Dailies Total1 (DT1)).
- To assess subjective ratings, cumulative comfort scores, average wear time and comfortable wear time while symptomatic CL wearers use their habitual DD CLs.
- To refit participants with DT1 CLs and assess subjective ratings, cumulative comfort scores, average wear time and comfortable wear time after wearing DT1 for one month.

Primary Endpoint:

- Subjective ratings of end-of-day comfort and dryness (with CLs; 0 to 100 scale)
- Average wear time (hours)
- Comfortable wear time (hours)

3 RATIONALE

Refitting symptomatic CL-wearing patients into daily disposable (DD) CLs is one problem-solving strategy that has been frequently reported.

To explore if the unique 'water gradient' material of DT1 allows symptomatic daily disposable contact lens wearers to comfortably wear these contact lenses for a longer period than possible in their habitual DD lenses.

4 HYPOTHESIS

DT1 CLs will provide equivalent or better end-of-day comfort and longer comfortable wear time for DD CL wearers who suffer from DED compared to their habitual lenses.

5 MATERIALS AND METHODS

5.1 STUDY DESIGN

5.1.1 OVERALL DESIGN

This is a prospective, single-site, non-randomized, participant masked (study lenses are over-labelled), comparative study (habitual DD vs DT1) including 43 symptomatic DD CL wearers with DED. Clinical signs and subjective symptoms with habitual lenses will be assessed at the screening visit and these results will be compared to the study lens after 1 month of wear.

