5.4.2 STUDY VISITS

Table 2 shows the summary of the 3 study visits.

Table 2: Summary of visits

Visit code	Visits
1	Screening (1.5 hours)
2	Review habitual DD lenses and dispense DT1, 6-14 days after V1 (1.0 hour)
3	Review DT1 and study exit, 29-34 days after V2 (1.0 hour)

Visit 1 (Day 0 for habitual DD): Screening (1.5 hours)

- Informed consent procedure

- Participants will attend this visit wearing their habitual spectacles. They will be asked to stop lens wear for \geq 12 hours prior to the visit and will be asked to bring a new pair of their habitual lenses with them.
- The purpose of this visit is to determine participant eligibility and to classify the type of DED exhibited by the participant, using TFOS DEWS II guidelines. These tests will include:
 - OSDI questionnaire (with participant reflecting on their ocular symptoms without CL wear);
 - Tear osmolarity (TearLab);
 - Non-invasive tear break-up time (using the Oculus K5M);
 - Tear meniscus height assessment (using the Oculus K5M);
 - Meibomian gland assessment (to calculate a meibomian gland score) using the meibomian gland evaluator (Johnson & Johnson Vision);
 - Ocular surface staining assessment and lid wiper staining;

To minimize disruption of the ocular surface, these tests will be conducted in the order of the least invasive, through to the most invasive.

- Participants will complete a CLDEQ-8 questionnaire to review their experience with their habitual lenses over the past two weeks.
- A full slit lamp biomicroscopy examination will also be performed to determine ocular health, including ocular hyperemia and surface staining with fluorescein.
- Participants will undergo a subjective refraction (Distance High Contrast High Illumination [HIHC] visual acuity, OD, OS & OU) and will be fit with DT1 to confirm acceptable visual acuity and lens fit.
- Participants will be asked to insert their habitual lenses to confirm acceptable visual acuity and lens fit.
 - Distance HCHI visual acuity with habitual lenses, OD, OS & OU
- If the participant meets all inclusion / exclusion criteria, the participant will be instructed to wear their habitual DD CLs as usual until their next scheduled visit.

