- Participants will be provided with a subjective rating questionnaire (related to comfort, dryness, handling, onset time of discomfort, total wear times and reasons for lens removal) to be completed at home on Days 1, 3 and 5. Participants will be instructed that they must wear the lenses on the days where they are required to complete the ratings, and will be scheduled to return for their next visit between 6 and 14 days after the screening visit.

Visit 2 (Day 0 for DT1): Review habitual DD lenses and dispense DT1, 6-14 days after V1 (1.0 hour)

- Participants will attend this visit wearing their habitual DD CLs for \geq 2 hours prior to the visit.
- The subjective ratings completed at home will be reviewed.
- In-office subjective ratings of a typical day for comfort, dryness, vision and handling (with CLs; 0 to 100 scale), plus total wear time and comfortable wear time (onset time of discomfort) per day over the last month.

- The following assessment of the habitual lenses will be made:
 - Distance HCHI visual acuity, OD, OS & OU;
 - Lens surface characteristics: wettability and deposition;
 - Lens fit.
- After lens removal, a slit lamp biomicroscopy examination (including assessments for ocular surface staining and hyperemia) will be performed.
- DT1 will be dispensed and the following assessments will be made:
 - Distance HCHI visual acuity, OD, OS & OU;
 - Lens surface characteristics: wettability and deposition;
 - Lens fit.
- Participants will be provided with a 1 month supply of overlabeled DT1 CLs (for masking) and instructed to wear the lenses at least 3 days per week and 6 hours per day throughout the study.
- Participants will be provided with a subjective rating questionnaire (related to comfort, dryness, handling wear times and reasons for lens removal) to complete at home on Days 1, 3, 5, 7, 21, 28. Participants will be instructed that they must wear the study lenses on the days where they are required to complete the ratings, and will be scheduled to return for their next visit between 29 and 34 days after V2.

Visit 3: Review DT1 and study exit, day 29-34 days after V2

- Participants will attend this visit wearing the study CLs for \geq 2 hours prior to the visit.
- Participants will be asked to complete a CLDEQ-8 questionnaire to review their experience with the DT1 study lenses.
- The subjective ratings completed at home will be reviewed.

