- In-office subjective ratings of comfort, dryness, vision and handling (with CLs; 0 to 100 scale), total wear time and comfortable wear time (onset time of discomfort) over the last month.
- The following assessment of the study lenses will be made:
 - Distance HCHI visual acuity, OD, OS & OU;
 - Lens surface characteristics: wettability and deposition;
 - Lens fit.
- Slit lamp biomicroscopy examination (including assessments for ocular surface staining and hyperemia).
- Study exit documentation & reimbursement.

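### Section 5.1.1 takes habitual-lens clinical signs from the lens-free screening visit, although wear-matched signs are collected at Visit 2; 5.1.1 and 11.1 should name Visit 2

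*Combined protocol and SAP*

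**What the plan says.** **Section 5.1.1 (overall design).** "Clinical signs and subjective symptoms with habitual lenses will be assessed at the screening visit". This is the only sentence in the document that pairs visits for clinical signs; its second half gives the other side of the pairing, namely that "these results will be compared to the study lens after 1 month of wear".

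**Section 5.4.2, Visit 1 (screening).** "Participants will attend this visit wearing their habitual spectacles". They are asked to stop lens wear for at least "12 hours prior to the visit and will be asked to bring a new pair of their habitual lenses with them". Then: "A full slit lamp biomicroscopy examination will also be performed to determine ocular health, including ocular hyperemia and surface staining with fluorescein". Insertion of the habitual lenses, to check acuity and fit, is listed after this. The stated purpose of the visit is eligibility and DED classification.

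**Section 5.4.2, Visit 2.** "Participants will attend this visit wearing their habitual DD CLs for" at least 2 hours. Wettability, deposition and fit of those lenses are graded. "After lens removal, a slit lamp biomicroscopy examination (including assessments for ocular surface staining and hyperemia) will be performed".

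**Section 5.4.2, Visit 3.** Participants arrive after at least 2 hours in DT1. Wettability, deposition and fit are graded, and the list continues with "Slit lamp biomicroscopy examination (including assessments for ocular surface staining and hyperemia").

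**Table 3 (section 5.5)** schedules biomicroscopy at all three visits, and habitual-lens fit, wettability and deposition at both Visit 1 and Visit 2.

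**Section 11.1** compares one month of DT1 with habitual wear and gives a general rule for testing differences between lenses. It does not say which visit supplies the habitual value. Table 4 lists CLDEQ-8 and subjective ratings but no clinical sign.

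**The concern.** A paired comparison of two lenses is interpretable only if the eye is examined in the same state under each. The pairing in 5.1.1 sets an eye that has had no lens for at least 12 hours against an eye that has worn DT1 for at least 2 hours. For wettability and deposits it sets a lens taken new from its package against a worn one.

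Any effect of wear itself on staining or hyperemia, and any build-up of deposits during wear, would then be reported as a difference between habitual lenses and DT1. The difference in wear state applies to every participant. Pairing does not remove it, and a larger sample would not dilute it.

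An analyst who follows 5.1.1 uses an unsuitable baseline. One who sets it aside must choose between Visits 1 and 2 without a rule, possibly after seeing the data.

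**Working it through.** **Step 1. The three visits side by side** (5.4.2 and Table 3; section 5.5 says that the order of procedures is the one in 5.4.2).

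| | Visit 1 | Visit 2 | Visit 3 |
|---|---|---|---|
| State on arrival | Spectacles, at least 12 h lens-free | Habitual lenses, at least 2 h | DT1, at least 2 h |
| Staining, hyperemia | Before habitual lenses are inserted | After removal of worn habitual lenses | After DT1 wear |
| Wettability, deposits | Habitual lens, newly inserted | Worn habitual lens (and DT1 at dispensing) | Worn DT1 lens |
| Stated role | Eligibility, DED classification | Review of habitual lenses, dispensing | Review of DT1, exit |

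The visit that 5.1.1 names cannot supply ocular signs under habitual wear. The visit that it does not name can.

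**Step 2. What each pairing estimates.** Write S for the mean of a sign.

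- Visit 3 − Visit 1 = S(DT1, worn) − S(lens-free)
- Visit 3 − Visit 2 = S(DT1, worn) − S(habitual, worn)
- The first minus the second = S(habitual, worn) − S(lens-free)

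The last line contains no DT1 term. It is the effect of habitual wear, plus any other change between Visits 1 and 2, and the pairing in 5.1.1 adds it to the lens comparison.

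**Step 3. Which measures are exposed.** The lens-free period matters for staining and hyperemia. The newly inserted lens matters for wettability and deposits. Osmolarity, break-up time, meniscus height and meibomian gland score are scheduled only at Visit 1, so no comparison with Visit 3 is possible and they are not at issue.

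**Step 4. Size.** The documents give no wear effect for any sign, so what follows is an illustration on assumed shifts. The plan's own figure comes first: for a two-sided paired t-test with diff/SD = 0.60 and α = 0.05 (section 5.2.1), exact power from the noncentral t distribution first reaches 0.95 at n = 39 (power 0.955). The stated 39 is reproduced. That calculation is for subjective ratings, and this point does not change it.

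Now take n = 39, no true lens effect, and a pure wear-state shift of b SDs of the paired difference. The probability of declaring a lens difference is the power of the same test with 38 degrees of freedom and noncentrality b × √39, where √39 = 6.245:

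| Assumed b | Noncentrality | Probability of a false lens difference |
|---|---|---|
| 0 | 0 | 0.05 |
| 0.2 | 1.249 | 0.23 |
| 0.4 | 2.498 | 0.68 |
| 0.6 | 3.747 | 0.95 |

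The table shows how error would grow if a shift exists. It is not evidence that one does.

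**The case against.** The strongest reply is that one overview sentence carries a wrong visit label and the operative schedule is sound. Visit 2 is set up as a review of the habitual lenses after wear, and Visit 3 mirrors it for DT1. The Visit 1 text already limits its purpose to eligibility and classification. Section 11.1 speaks of habitual wear, which a lens-free examination cannot represent, and Table 4 commits to no test of signs. The objectives that compare lenses, the hypothesis and the sample size all rest on ratings and wear times.

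Most of this stands, and it limits the point to a conflict in the text over secondary measures. It does not remove the point, because nothing in 11.1 overrides 5.1.1, and the general rule in 11.1 is wide enough to cover signs.

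Four stronger readings are tempting and are not supported:

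- *The trial has no valid comparison of signs.* It has one, Visit 2 against Visit 3; the plan does not name it.
- *The bias runs against DT1.* The direction is unknown. Staining is one route to eligibility (inclusion criterion 4c), so values at the selecting visit may fall later by regression to the mean, which would favour DT1. The other tests at Visit 1 could also disturb the ocular surface.
- *Efron grading in 0.1 steps makes a small shift detectable.* Step size says nothing about grader variability.
- *Lens fit is equally compromised.* At Visit 1 fit is judged with the lens in place, so the 12-hour period has little bearing on it.

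**Conclusion.** The point holds as a conflict between 5.1.1 and the visit schedule, left unresolved by 11.1. If followed as written, 5.1.1 confounds lens with wear state for staining and hyperemia, and worn with newly inserted lenses for wettability and deposits.

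Severity is minor to moderate. Only secondary comparisons of signs are exposed, and the size and direction of the bias cannot be obtained from the documents. A reader might infer that the primary result is at risk. It is not affected by this point: the primary endpoints are end-of-day comfort and dryness ratings, average wear time and comfortable wear time (section 2), none of which is a slit-lamp or lens-surface grade. Section 5.4.2 differs from Table 3 and 5.5.2 on the visit for in-office habitual-lens ratings, but that is a separate matter.

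The conclusion assumes that the Visit 1 procedures are done in the order listed in 5.4.2, as section 5.5 says, and that signs will be compared between lenses, as 5.1.1 says.

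**What to change.** 1. In 5.1.1, replace the screening visit with Visit 2 as the source of habitual-lens clinical signs.
2. In 11.1, add a line such as: *Slit-lamp staining and hyperemia, and lens wettability and deposits, are compared between Visit 2 (habitual lens, after wear) and Visit 3 (DT1, after wear). Visit 1 signs are used only for eligibility and DED classification.* For wettability and deposits, specify the grade of the worn habitual lens at Visit 2, because DT1 is also graded there at dispensing.

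The cost is wording in two sections, ideally settled before the data are analysed. No new data, visits or participants are needed, since the Visit 2 measurements are already scheduled.

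The change removes the planned difference in wear state. It does not remove the fixed order of lenses, which follows from the non-randomized design. Matching appointment times or recording hours of wear at Visits 2 and 3 would be an optional refinement, since both set only a 2-hour minimum; this correction does not depend on it.

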5.1.2 RANDOMIZATION

There will be no randomization in this study.

5.1.3 MASKING

Participants will be masked to the lens type (brand) they will be wearing during the study in order to reduce bias towards or against this product. Lens packages/ blister will be overlabeled.

5.2 STUDY POPULATION

5.2.1 SAMPLE SIZE CALCULATION

The sample size required for a 2-tailed matched paired t-test to detect a difference of at least 5 points in subjective ratings, with $\alpha=0.05$, power = 0.95, and $\text{diff}/\text{SD} = 0.60$ is 39 (Figure 1).

Therefore, a sample size of 43 is being proposed to account for possible dropouts and screen failures (for which not all visits are required).

[figure not shown]

Figure 1: Sample size calculation

5.2.2 NUMBER OF PARTICIPANTS

Up to 60 participants may be screened using CORE records and advertising approved by the UW Office of Research Ethics. Approximately 43 participants will be dispensed / randomized with study products, with a target of number of 39 participants completing the study. Informed consent will be obtained for all participants prior to their enrolment in the study (Appendix 1).

5.2.3 INCLUSION AND EXCLUSION CRITERIA

A person is eligible for inclusion in the study if he/she:

1. Is at least 17 years of age and has full legal capacity to volunteer;
2. Has read and signed an information consent letter;
3. Is willing and able to follow instructions and maintain the appointment schedule;
4. As per TFOS DEWS II², have dry eye symptoms (without CL wear) as determined by an OSDI score of ≥ 13 and at least **one** of the following:
 - a. Tear osmolarity $\geq 308\text{mOsm/L}$ or interocular difference $>8\text{ mOsm/L}$
 - b. Non-invasive tear breakup time of < 10 seconds in at least one eye
 - c. More than 5 spots of corneal staining OR > 9 conjunctival spots in at least one eye
5. Reports dryness while wearing DD CLs with CLDEQ-8 score ≥ 12 and $\leq 20^3$
6. Habitually wears soft spherical DD CLs with a power between +6.00D and -10.00D
7. Manifest spectacle cyl $\leq 1.00\text{DC}$ in either eye
8. BCVA $\leq 0.20\text{ log MAR}$ each eye with habitual & DT1
9. Acceptable fit with habitual & DT1
10. Willing to wear DT1 CLs at least 3 days per week and 6 hours per day throughout the study

A person will be excluded from the study if he/she:

1. Is participating in any concurrent clinical or research study;
2. Has any known active* ocular disease and/or infection;
3. Has a systemic condition that in the opinion of the investigator may affect a study outcome variable;
4. Is using any systemic or topical medications that in the opinion of the investigator may affect a study outcome variable;
5. Has known sensitivity to the diagnostic pharmaceuticals to be used in the study;
6. Is pregnant, lactating or planning a pregnancy at the time of enrolment (by self-report);

7. Is aphakic;
8. Has undergone refractive error surgery;
9. Has taken part in another clinical research study within the last 14 days;
10. Current habitual wearer of DT1
11. Any ocular and/or systemic conditions or concomitant medication to contraindicate contact lens wear or be expected to interfere with the primary outcome variables.

* For the purposes of this study, active ocular disease is defined as infection or inflammation which requires therapeutic treatment. Mild (i.e. not considered clinically relevant) lid abnormalities (blepharitis, meibomian gland dysfunction, papillae), corneal and conjunctival staining and dry eye are not considered active ocular disease. Neovascularization and corneal scars are the result of previous hypoxia, infection or inflammation and are therefore not active.

5.2.4 REPEATED SCREENINGS

In some circumstances a repeated screening may need to be scheduled. Examples include, but are not limited to:

1. Incomplete information available at time of screening to determine eligibility (e.g. current lens brands worn, history from current eye care practitioner etc.)
2. Study procedures unable to be completed in time scheduled for visit;
3. Study products not available at the time of the screening visit;
4. A transient health condition which may affect the eye(s) (e.g. a common cold, active allergies, fatigue etc;)
5. The short term use of medications (e.g. antibiotics, antihistamines etc.)
6. Reassessment of baseline ocular conditions (e.g. corneal and/or conjunctival staining, scars etc.)

The maximum total number of screenings permitted (per subject) will be 3.

5.3 STUDY MATERIALS

5.3.1 LENSES

Details on the lens type used in this study are listed in Table 1.

Table 1: Lens characteristics

Lens	Lens name
Material	Dailies Total1
Manufacturer	Alcon
HC licence #	87774
Dk/t (barrer/cm)	156 (-3.00D)
Sphere power (D)	+6.00D to -10.00D
Base curve (mm)	8.5
Diameter	14.1
Replacement schedule	daily

5.3.2 LENS CARE SYSTEM

A lens care system is not needed, because the lenses will be worn on a daily disposable basis and will be discarded at the end of each lens wear day.

5.3.3 REWETTING DROPS

Participants will not be encouraged to use rewetting drops; however, those who habitually used rewetting drops will be allowed to continue using their normal drops. Rewetting drop use will be recorded at each visit.

5.3.4 ORDERING CONSUMABLES

DT1 lenses will be supplied by Alcon for the use in this study. Osmometry chips will be invoiced for upon completion of the study and are a direct consumable cost that is not included in the budget.

5.3.5 DISPOSING OF CONSUMABLES

Worn lenses collected during study visits will be discarded as per University of Waterloo regulations.

5.3.6 PRODUCT ACCOUNTABILITY

Accountability logs will be kept to include the number of lenses received, dispensed and unused. All products dispensed to participants will be recorded in the study binder.

5.4 SCHEDULED AND UNSCHEDULED VISITS

This study has a total of 3 study visits, including the screening visit.

Pre-screening:

Potential participants who show an interest in the study will be provided with more details about the study over the phone as well as in writing (Recruit 01 Recruitment email). Two prescreening questionnaires (Appendix 4 CLDEQ-8: Symptoms with lens wear and Appendix 5 OSDI: Dry-eye symptoms without lens wear) will be attached to the email script and sent to participants in the CORE database or to participants expressing an interest in the study. These completed questionnaires will be used to determine whether the subject is likely to meet the dry eye symptom eligibility criteria. If interested, potential participants can return both questionnaires to CORE, in order to determine whether they may generally be suitable for the study based on the severity of their dry eye symptoms. Participants meeting the dry eye symptom criteria, according to the questionnaires, will be invited to a screening visit where their full eligibility will be determined. Questionnaires completed prior to the consent procedure will not be included in the analysis, instead the questionnaires will be completed again during the Screening visit. Participants may also be accepted to participate in the study without previously completing the questionnaires, however in order to save time and to avoid screen failures due to insufficient symptoms, completing the questionnaires prior to the screening visit is preferred.

5.4.1 SCREENING

The investigator will determine participant eligibility using the inclusion and exclusion criteria. All participants who sign the consent letter will be assigned a study ID number. Ineligible participants will be discontinued from the study.

